## 8. Investigational Plan

### 8.1. Summary of Study Design

[figure not shown]
Study H9H-MC-JBAS is a 3-arm, randomized, multicenter, global (Asia), Phase 2 study of LY2157299 plus sorafenib therapy or LY2157299 monotherapy compared to sorafenib plus LY2157299-matched placebo therapy in patients with relapsed or progressed HCC. Patients who receive sorafenib and investigators will be blinded to the LY2157299 or placebo assignment for those arms.

Approximately 120 patients will be randomly assigned in a 1:2:1 fashion to 1 of 3 treatment arms: LY2157299 monotherapy, LY2157299 plus sorafenib 400 mg BID, or sorafenib 400 mg BID plus LY2157299-matched placebo ([Figure JBAS.8.1](#)). The monotherapy dose will be 150 mg BID (300-mg daily dose) for 14 days, followed by 14 days with no study drug. The LY2157299 dose used in combination with sorafenib will be determined based on the results of the JBAK study – Part C (dose will either be 80 mg or 150 mg BID [160-mg or 300-mg daily dose]). LY2157299 and matched placebo will be given for 14 days followed by 14 days of rest; sorafenib will be given each day during the cycle. A cycle is defined as 28 days in duration (a minimum of 26 days and a maximum of 31 days). The treatment period for LY2157299 must be a minimum of 10 days and a maximum of 14 days.

Patients may receive treatment until they met at least one of the discontinuation criteria ([Section 7.3.1](#)).

This Phase 2 study will be considered complete after 100 deaths for OS analysis have occurred. Patients still on treatment at the time that the study is considered complete may enter the treatment extension period and continue with the study treatment (see [Section 8.1.1](#)).

End of study (trial) is the date of the last visit or last scheduled procedure shown in the Study Schedule ([Attachment 1](#)) for the last active patient in the study. Consult regional standard operating procedures for further information.

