#### **10.3.2.2. Echocardiographs with Doppler and Chest Computed Tomography Scans**

Because of the cardiotoxicity monitoring in this study, echocardiographs with Doppler and chest CT scans are being performed (see [Attachment 1](#), [Attachment 14](#), and [Attachment 15](#)).

Echocardiography with Doppler will be locally assessed at screening for enrollment and throughout the study according to the Study Schedule ([Attachment 1](#)) for safety decisions by a physician or a person who is qualified by experience or training. The individual must be identified at each site. A central reading will be performed for the data used in the study report.

Chest CT scan with contrast of thorax and abdomen to evaluate the large vessels of the heart will be locally assessed at screening for enrollment and every 6 months throughout the study and at the end of study visit (Visit 801) according to the Study Schedule ([Attachment 1](#)) for safety decisions by a physician or a person who is qualified by experience or training. Alternatively, chest and/or abdomen MRI are allowed.

Chest CT scan with contrast of thorax and abdomen for tumor assessment will be locally assessed at screening for enrollment and every 6 weeks starting Cycle 2 Day 14 until radiological disease progression according to the Study Schedule ([Attachment 1](#)) by a physician or a person

who is qualified by experience or training. Alternatively, chest and/or abdomen MRI are allowed.

If the patient has clinically significant cardiac findings at discontinuation (Visit 801), echocardiography, ECG and ECG chemistry will be repeated every 2 months for 6 months (Visits 803, 804, and 805).

If there are no clinically significant cardiac findings at discontinuation (Visit 801), 1 more echocardiography, ECG, and ECG chemistry will be performed after 2 months (Visit 802). If a patient receives another treatment, Visit 802 cardiac assessments will not be performed.

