## **Attachment 1. Protocol JBAS Study Schedule**

---

Study Schedule, Protocol H9H-MC-JBAS – Study Period

Cycle (Visit)	Baseline (Visit 0)			Patient on Study Treatment									Post Discontinuation Follow-Up Periods		Comments	
				Cycle 1 (Visit 1)			Cycle 2 (Visit 2)			Cycle 3, n a (Visit 3, etc)			30-Day Safety Follow-Up (v801)	Long-Term Follow-Up b (v802, v803, etc)		
Relative Day Within a Cycle	≤28	≤14	≤7	1c,d	8c	14c	15	22	1c	14c,e	22	1c			14c,e	
Procedures																
Informed consent	X															Informed consent must be signed prior to performing any study procedures.
Medical history		X														
Child-Pugh, BCLC, and CLIP staging			X f													
Physical exam including vital signs (heart rate, blood pressure, weight)		X		X		X			X	X		X		X		Starting in Cycle 3, to be performed once per cycle
CTCAE grading		X		X		X			X	X		X		X	X g	Starting in Cycle 3, to be performed once per cycle
Concomitant medications		X		X					X			X	X	X	X	During long-term follow-up collect only therapy provided to patient for HCC
ECOG performance status		X		X		X			X	X		X		X		Starting in Cycle 3, to be performed once per cycle
Survival data														X		Every 60 days ±7 days

Cycle (Visit)	Baseline (Visit 0)			Patient on Study Treatment									Post Discontinuation Follow-Up Periods		Comments	
				Cycle 1 (Visit 1)			Cycle 2 (Visit 2)			Cycle 3, na (Visit 3, etc)			30-Day Safety Follow-Up (v801)	Long-Term Follow-Up b (v802, v803, etc)		
Relative Day Within a Cycle	≤28	≤14	≤7	1 c,d	8 c	14 c	15	22	1 c	14 c,e	22	1 c			14 c,e	
Tumor assessment, physical (palpable or visible)		X		X					X			X		X		
Imaging procedures																
Echocardiography with Doppler h	X								X			X		X i	X i	Cycle 2, 3, 4, and every other cycle (Cycle 6, Cycle 8, etc)
Chest CT scan or Chest MRI		X												X j		CT scan or MRI every 6 months (for cardiac assessment)
Tumor assessment, radiological		X								X			X	X k	X k	Chest CT scan with contrast of thorax and abdomen ( with both arterial and portal phase imaging of the liver for mRECIST) or MRI for tumor assessment every 6 weeks (± 3 days) starting Cycle 2 Day 14
ECG		X							X			X		X i	X i	Cycle 2, 3, 4, and every other cycle (Cycle 6, Cycle 8, etc)

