### Confirmatory Measurement/Duration of Response

#### *Confirmation*

The main goal of confirmation of objective response in clinical trials is to avoid overestimating the response rate observed. The confirmation of response is particularly important in *nonrandomized trials* where response (CR/PR) is the primary end point. In this setting, to be assigned a status of PR/CR, changes in tumor measurements must be confirmed by repeat assessments that should be performed no less than 4 weeks after the criteria for response are first met. To confirm a response of CR, a full assessment of all target and nontarget lesions that were present at baseline must occur, including those measured by bone scan. To confirm a PR or SD, a full assessment of target lesions that were present at baseline must occur; assessment of nontargets is not required.

However, in *randomized trial* (Phase 2 or 3) or studies where SD or progression is the primary endpoint, confirmation of response is not required. But elimination of the requirement may increase the importance of central review to protect against bias, in particular of studies which are not blinded.

In the case of SD, follow-up measurements must have met the SD criteria at least once after start of treatment at a minimum interval not less than 6 weeks measured from the first dose.

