Screen failures	Patients who have signed informed consent, do not meet eligibility criteria and are not treated/randomized.
Randomized	Patients who have been assigned to study treatment but may have not received any study treatment (LY2157299, LY2157299-matched placebo, or sorafenib).
Patients on therapy	Patients who have been randomized to study treatment and have received at least 1 dose of study treatment (LY2157299, LY2157299-matched placebo, or sorafenib).
Study day	If assessment is on or after date of first treatment dose then (date of assessment) – (date of first study treatment dose) + 1 If assessment precedes first treatment dose then (date of assessment) – (date of first study treatment dose) There is no study day 0. Study day 1 is the date of first dose and study day -1 is the day before the first dose.
Cycle day	If assessment is on or after date of first treatment dose then (date of assessment) – (date of first study treatment dose in cycle) + 1 If assessment precedes first treatment dose then (date of assessment) – (date of first study treatment dose in cycle) There is no cycle day 0. Cycle day 1 is the date of first dose in the cycle and cycle day -1 is the day before the first dose.
Baseline	For change from baseline analysis, baseline value is defined as the last reported measure on or before the first dose date (or discontinuation, if no treatment is given). For change from baseline within a cycle, the measure prior to the first dose if that cycle is baseline.
Study treatment period	Time from treatment start to discontinuation from study treatment
Post-discontinuation – short-term follow-up	The short term follow-up period begins 1 day after discontinuation of study treatment and lasts approximately 30 days (Visit 801).
Post-discontinuation – long-term follow-up	The long-term follow-up period begins 1 day after the short-term follow-up period (Visit 801) is completed and continues until death to collect survival data.

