- **Overall Response Rate (ORR)** is defined as the proportion of patients who achieved a best overall response of either complete response (CR) or partial response (PR). The overall response rate for each treatment group will be estimated by dividing the total number of responders by the number of patients qualifying for the tumor response qualified population (Section 6.11). Response will be evaluated based on the RECIST version 1.1 and mRECIST criteria. No confirmation of response is required. Overall response rate will be calculated separately for each evaluation criteria.
- **Disease Control Rate (DCR)** is defined as the proportion of patients who achieved a best response of CR, PR or stable disease (SD). This rate will be estimated for each treatment group by dividing the total number of patients that had CR, PR or SD by the number of patients qualifying for the tumor response qualified population (Section 6.1.1). Best response of SD is defined as disease that does not meet the criteria for CR, PR, or progressive disease (PD) and has been evaluated at least one time, and at least 6 weeks after

baseline assessment. Patients without a valid response assessment at least 6 weeks after baseline assessment are assigned a best response of nonevaluable unless progression has already occurred. Response will be evaluated based on the RECIST version 1.1 and mRECIST criteria. Disease Control Rate will be calculated separately for each evaluation criteria.

All time-to-event endpoints will be analyzed using the Kaplan-Meier method. Covariates may also be included in these time-to-event models to account for variation in survival time. A Bayesian model will be used to estimate the hazard ratio of overall survival between the treatment arms.

Table JBAS.6.3. An Overview of the Efficacy Analyses

Efficacy Endpoint	Statistical Analysis	SAS Procedures
Primary analysis:		
Overall survival (OS)	A Bayesian OS model to estimate the hazard ratio (HR) of OS (under strong prior) and 90% predictive interval between LY2157299 plus sorafenib therapy and sorafenib plus placebo therapy	Non SAS - FACTS
Secondary analyses:		
Overall survival	The same Bayesian OS model in the primary analysis will be repeated using a weak prior.	Non SAS - FACTS
	The same Bayesian OS model in the primary analysis is used in secondary analysis to estimate the HR between LY2157299 monotherapy and sorafenib plus placebo therapy	Non SAS - FACTS

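### The 6-week minimum for stable disease runs from the baseline scan in the SAP and from first dose in the protocol, and neither allows for the first scan's window, so a few compliant first scans miss disease control rate

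*SAP*

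**What the plan says.** **SAP 6.9 (Disease Control Rate).** The rate is the share of the tumor response qualified population whose best response is CR, PR or SD. SD must have been assessed at least once, 6 weeks or more after the baseline assessment. The SAP then adds: "Patients without a valid response assessment at least 6 weeks after baseline assessment are assigned a best response of nonevaluable", with an exception for those who have already progressed.

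**Protocol Attachment 9 (Confirmation).** The SD criteria must be met at least once "at a minimum interval not less than 6 weeks measured from the first dose".

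**Scan timing.** The Study Schedule (Attachment 1) sets radiological tumor assessment "every 6 weeks (± 3 days) starting Cycle 2 Day 14". Protocol 10.3.2.2 gives the same start without the window. Protocol 8.1 sets a 28-day cycle and permits 26 to 31 days.

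**Day counting and baseline.** SAP Table JBAS.6.1 states: "There is no study day 0. Study day 1 is the date of first dose". For change-from-baseline analyses, the same table says the "baseline value is defined as the last reported measure on or before the first dose date", which allows a baseline on the day of dosing. The baseline scan sits in the column for 14 days or less in Attachment 1, while Attachment 9 allows up to 4 weeks before treatment.

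Neither document attaches a tolerance to the 6-week rule or says which clock prevails.

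**The concern.** SAP 6.9 evaluates response by RECIST 1.1, and the study's RECIST 1.1 text is Attachment 9. A programmer deriving best response therefore has two instructions that can classify the same scan differently. The first scheduled scan also falls almost exactly on the 6-week mark, so a few days of permitted variation can decide whether a patient is SD or nonevaluable.

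Under the SAP clock, two patients scanned on the same study day can be classified differently only because their screening scans were taken on different dates. An affected patient stays in the denominator of the disease control rate but leaves the numerator. The rate is reported by arm with an exact 95% interval, separately for RECIST 1.1 and mRECIST. If the clock is left open, someone will choose it after the scan dates are known.

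**Working it through.** The documents give no figure for this effect, so there is nothing to reproduce. The check is calendar arithmetic followed by an illustrative size.

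**Inputs**
- Cycle 1 length L: 28 days, permitted 26 to 31 (Protocol 8.1).
- First scan: Cycle 2 Day 14, window w = -3 to +3 days, then every 6 weeks (Attachment 1).
- Threshold: 6 weeks = 42 days.
- Baseline scan k days before first dose: k up to 14 (Attachment 1).
- Median TTP on sorafenib: 2.8 months in the Asia-Pacific trial and 5.5 months in the US/EU trial (Protocol 5).
- Assumptions: dates spread evenly over their windows; exponential TTP counted from first dose; every patient progression-free at scan 1 is SD; all patients are in the denominator. The documents give no distribution of scan dates.

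**Step 1. Day of the first scan.** Elapsed days after first dose = L + 13 + w.

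| Cycle 1 length | Nominal | Window | Days failing, elapsed count | Days failing, inclusive count |
|---|---|---|---|---|
| 26 | 39 | 36–42 | 6 of 7 | 5 of 7 |
| 28 | 41 | 38–44 | 4 of 7 | 3 of 7 |
| 31 | 44 | 41–47 | 1 of 7 | 0 of 7 |

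The last two columns apply Attachment 9's clock. The inclusive count takes first dose as day 1, so a 28-day cycle puts the nominal scan on day 42.

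**Step 2. SAP clock, 28-day Cycle 1.** Days from baseline scan = 41 + w + k, and the scan fails if this is below 42.
- k = 0: 4 of 7 window days fail, including the nominal day.
- k = 1, 2, 3: 3, 2 and 1 of 7 fail, all of them early scans.
- k = 4 or more: none fail.

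For k = 1 to 14, the failures are 3 + 2 + 1 = 6 of 14 × 7 = 98, or 6.1%. The inclusive count gives 2 + 1 = 3 of 98. Adding same-day baselines (k = 0) gives 10 of 105, or 9.5%. On that grid the first-dose clock fails 60 of 105, and the two clocks disagree on 50 of 105. With a 26-day Cycle 1 the earliest scan is day 36, so failure is possible up to k = 5 (36 + 5 = 41).

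The SAP clock also works in the other direction. A scan 28 days after first dose, with a baseline 14 days before, reaches 42 and would count as SD. No scan is scheduled then, so this case needs an unscheduled scan.

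**Step 3. Who is affected.** The second scan is due at 41 + 42 = 83 days (80 to 86) and satisfies either rule. Only patients whose sole non-progression assessment is the first scan can be reclassified. The share progressing between the two scans is exp(-41h) - exp(-83h), with h = ln 2 / (median × 30.44 days):
- 2.8 months: h = 0.00813; 0.717 - 0.509 = 0.207.
- 5.5 months: h = 0.00414; 0.844 - 0.709 = 0.135.

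**Step 4. Loss of disease control rate, 28-day Cycle 1**

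| Clock | Share failing | At 2.8 months | At 5.5 months |
|---|---|---|---|
| SAP, k = 1–14 | 6/98 | 1.3 points | 0.8 points |
| SAP, k = 0–14 | 10/105 | 2.0 points | 1.3 points |
| Attachment 9, inclusive | 3/7 | 8.9 points | 5.8 points |
| Attachment 9, elapsed | 4/7 | 11.8 points | 7.7 points |

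For scale, one reclassified patient is 1/30 = 3.3 points in a 30-patient arm and 1/60 = 1.7 points in the combination arm. A loss of 1.3 points is 0.013 × 30 = 0.4 of a patient.

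**The case against.** The strongest reply is that the conflict hardly reaches the reported result. Disease control rate is not among the protocol's objectives (6.2) or in its endpoint table (JBAS.10.1). It exists only in the SAP, with its own clock and its own nonevaluable rule. No test or decision rule uses it. At 15 responders of 30, the exact 95% interval runs from about 31% to 69%, so a point or so is lost in the noise. Patients who stop drug without progression continue to be scanned every 6 weeks, and a later SD scan cures the problem.

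All of that stands, and it sets the size of the point. It does not remove the contradiction. The SAP never says that its SD clock overrides the RECIST attachment it relies on, and its own rule still rejects some in-window scans. Nor does continued scanning help a patient who progresses before the second scan, or who starts new anticancer therapy, at which point Attachment 9 closes best response.

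A reader might also infer that a scan on its scheduled day is always one day short under Attachment 9. That holds only when elapsed days are counted. On the SAP's inclusive study-day convention the nominal scan is day 42 and passes.

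**Conclusion.** The point holds as a minor inconsistency in a descriptive secondary endpoint. The two documents start the 6-week clock at different dates and neither fits the scan window. Under the SAP rule, which governs, the loss is about 6% of scan-date combinations and roughly 1 point of disease control rate (up to about 2 if same-day baselines are included). These figures rest on a 28-day Cycle 1, evenly spread dates and exponential TTP. They count permitted combinations and do not forecast how many patients will be affected.

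Three stronger readings are not supported:
- **That the reported rate will be 6 to 12 points too low.** This needs Attachment 9's clock to be programmed for an endpoint that only the SAP defines.
- **That comparisons between arms are biased.** All arms share one scan schedule and the documents show no difference in scan timing.
- **That the protocol's first-dose clock also governs mRECIST.** The text of Attachment 16 is not visible, so this cannot be judged.

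OS, TTP, PFS and ORR do not use the rule. Best overall response is affected only in its patient listing (SAP 6.9.2.2).

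**What to change.** In SAP 6.9, change both sentences (the SD definition and the nonevaluable rule) to a single clock measured from first dose. State that it prevails over Attachment 9, and give it a tolerance equal to the scan window. For example: best response of SD requires an evaluable assessment that is not CR, PR or PD, at or after the opening of the Cycle 2 Day 14 window, which is at least 36 elapsed days after first dose. The 36 comes from the shortest permitted Cycle 1 and the earliest window day: 26 + 13 - 3 = 36. State that days are elapsed, so that the counting convention is no longer open. Align Attachment 9 at the next protocol amendment.

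The cost is two sentences in the SAP now and one in the protocol later, with no new data. The downside is that the nominal SD minimum drops from 42 to 36 days. With a 28-day Cycle 1, a flat 36-day rule also admits scans on days 36 and 37, just before the window opens on day 38. Tying the rule to each patient's own Cycle 2 Day 11, the day the window opens, would avoid that.

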6.9.1. Primary Outcome and Primary Methodology

A method of analysis for comparing OS between the treatment arms will use a Bayesian exponential-likelihood model on treatment effects. The model incorporates historical data from 2 studies with a sorafenib plus placebo arm to augment the prospective control arm data. If the Bayesian posterior probability of superiority of the combination arm (LY2157299 plus sorafenib) over the control arm (sorafenib plus placebo) (that is, $HR < 1$) exceeds 0.84 under a strong prior, then it will be concluded that the combination arm is superior.

6.9.2. Secondary Efficacy Analyses/Outcomes/Comparisons

6.9.2.1. Additional Analyses of the Primary Outcome

The same Bayesian analysis as described in Section 6.9.1 will be repeated using the weak prior. The same Bayesian analysis will also be carried out to provide the hazard rates and ratios including 90% predictive intervals of the HR between LY2157299 monotherapy and sorafenib plus placebo therapy.

In addition to the above primary Bayesian analyses for OS, OS curves for each treatment arm will also be analyzed using the Kaplan-Meier product-limit method (Kaplan and Meier 1958). Two-sided, 95% CIs for median OS will be computed by the Brookmeyer and Crowley method (Brookmeyer and Crowley 1982). OS rates at 6 and 12 months will also be estimated using Kaplan-Meier estimates on the OS curve for each treatment arm. Associated 2-sided 95% CIs will also be calculated. Kaplan Meier plots of survival for each treatment group will also be provided.

Pairwise HRs along with 95% CIs between the 3 arms will be estimated using a stratified univariate proportional hazards (PH) model. Additional exploratory analyses using a PH model to control for other factors may be performed, including, but not limited to, ECOG performance status, portal vein thrombosis (yes vs. no), extra hepatic spread (yes vs. no), baseline AFP levels (<200 vs. ≥ 200 , <400 vs. ≥ 400), etiology and TGF- β levels (<3400 pg/ml vs. ≥ 3400 pg/ml). A stepwise procedure for variable selection will be applied. The univariate and multivariate analyses using PH models will be repeated on the safety population (Section 6.1.1) to explore the actual drug effect.

6.9.2.2. Efficacy Analyses of the Secondary Outcomes

Investigator-determined TTP, PFS and TTP/PFS rates will be summarized (at 3 months, 6 months, 9 months, 12 months) using Kaplan-Meier estimates of the median survival times (including 95% CIs). Pairwise HRs along with 95% CIs between the 3 arms will also be provided using stratified PH models. Additional exploratory analyses using PH models to control for other factors may be performed.

Investigator-determined ORR based on RECIST version 1.1 and mRECIST criteria will be estimated by dividing the total number of responders (complete response [CR] or partial response [PR]) by the number of who received at least 1 dose of study treatment and had measurable disease at baseline. Exact 95% CIs by the method of Clopper and Pearson (Clopper and Pearson 1934) for each treatment arm will be provided.

Investigator-determined response (using RECIST version 1.1 and mRECIST criteria) will be listed by patient and cycle. Tumor measurements by patient, cycle, and lesion will be listed. A separate listing will include changes from baseline in the sum of tumor measurements (over all lesions) and clinical assessments by patient and cycle. Efficacy parameters (OS, TTP, best overall response [BOR], minimum percent change from baseline of sum of lesion measurements) will be listed by patient. Additionally, a listing of disease status at the end of the study will be provided.

The listings and summary described above for investigator-determined assessments will be repeated for central readers' assessments when data are available.

All analysis described in this section will be conducted using the Tumor Response Qualified Population grouped based on randomized treatment assignment and repeated using the actual treatment (Section 6.1.1).

